Yo Puedo! Diabetes Self-Management Education + mHealth in Mexico City

NCT # 03159299

October 17, 2018

STUDY OBJECTIVES

- 1. To translate an evidence-based diabetes self-management education (DSME) program, Yo Puedo!, to the cultural norms, expertise of providers, and systems of care in Seguro Popular clinics in Mexico. The program will be adapted through a collaborative team of diabetes experts in the US and Mexico, Seguro Popular clinic administrators, physicians, nurses and adults with type 2 diabetes (T2D) in Mexico City, Mexico. This will include development and testing of a theory-based mHealth (pictorial text-messaging) component.
- 2. To evaluate the feasibility (process of implementation, fidelity of sessions, attendance, attrition), acceptability (interviews with program instructors, participants) and preliminary efficacy of Yo Puedo!+mHealth in adults with T2D in Mexico City. We will use a randomized, controlled pilot study design in which 60 adults with T2D are randomized to the Yo Puedo! + mHealth or a wait-list control condition with the hypothesis that clinical [A1C, body mass index (BMI), waist circumference (WC), blood pressure (BP)], T2D self-management, and self-efficacy outcomes will be greater in Yo Puedo!+mHealth participants compared to the wait-list control condition at 3 and 6 month follow-up. We also hypothesize that the Yo Puedo! + mHealth program is feasible and acceptable to adults with T2D and providers and that fidelity of the program will be maintained.

DESIGN

We will use a randomized, controlled pilot study design in which 60 adults with T2D are randomized to the Yo Puedo + mHealth or wait-list control condition with the hypothesis that clinical (A1C, BMI, BP), T2D self-management, and self-efficacy outcomes will be greater in Yo Puedo + mHealth participants compared to the wait-list control condition at 3 and 6 month follow-up. We also hypothesize that the Yo Puedo + mHealth program is feasible and acceptable to adults with T2D and providers, and that fidelity of the program will be maintained. Those in the control group will be invited to participate in the program after completion of the 6-month data collection. We will reconsent control group participants who chose to participate in the program after the 6-month data collection to have data collected one more time, approximately 3 months after the first class. Participants will be consented for this additional data collection in person at the last session of classes or prior to the data collection session itself. We will conduct interviews with the program instructors, participants, and select clinic personnel to identify barriers, facilitators, and acceptability of the program from multiple perspectives, recognizing the complexity of the health care system. Detailed notes on the process of implementation will be carefully recorded with the purpose of identifying successful and unsuccessful components of the program (positive and negative feedback loops in a complex system).

Setting. The study will be conducted in up to 10 Seguro Popular clinics. These clinics are part of the Sistema de Protección Social en Salud in Mexico. Individuals who obtain health care at these clinics are covered by public health insurance (Seguro Popular), and the services they get for T2D care include medical visits, referrals to specialists and nutritionist when needed, laboratory testing, and free medicines. The medical visits include medication prescription, blood pressure management, lipid monitoring, and eye/foot care. Laboratory analyses vary from patient to patient but generally includes 3 annual tests of A1C, although other glucose, urine, and lipids tests are also available. Patients with complications are referred to specialized health centers.

Interventions. All participants will receive standard T2D care at a Seguro Popular clinic as described above. The wait-list control condition group will receive a handout on T2D self-management and the opportunity to participate in the *Yo Puedo!* + mHealth program at the completion of 6-month data collection. The *Yo Puedo!* + mHealth DSME program includes: a) six

interactive group-based sessions (plus an initial orientation session) led by the program instructors on T2D self-management that is culturally relevant and at a low health literacy level (*Yo Puedo!* protocol adapted for Mexican context; see Table 1); b) behavioral support to collaboratively problem-solve barriers to change; and d) empowerment-based strategies to facilitate provider-patient communication. The *Yo Puedo!* program will be supplemented by one way text messaging provided by a web-based platform with privacy and security rules, which allows for automated and personalized messages and a database to store all messages. Automated daily text messages will include messages to promote understanding of T2D self-management, self-efficacy, and adherence to self-management goals. All text messages sent will initially be stored in the text messaging platform but will be archived to the REDcap database for subsequent data analysis. Participants in this group will also receive blood glucose monitors and will be instructed on how to use them as a part of the instruction provided in the Yo Puedo curriculum. The in-person component will be 6 weeks; daily text messaging will be for 6 months.

Participants will be randomized to a treatment condition in a 1:1 allocation ratio to one of the two treatment conditions using a computer-generated, block randomization procedure. Sequentially numbered opaque sealed envelopes will be used to conceal the allocation determination. The RA will inform participants about their treatment condition and protocol. After a group of 5 participants have been randomized to the *Yo Puedo!* + mHealth condition, the program will start. Within one week, participants will start the group sessions provided by the program instructors. The content and procedures in all sessions will be documented. Approximately 10% of sessions will be attended by one of the site Co-ls to evaluate protocol fidelity. The CHWs/MAs will remind participants about upcoming sessions at the end of a current session and will send a text or call participants the day before their next session. Attendance will be recorded. Written content from missed group sessions will be given to participants who will be asked to review at home and clarify questions with the program instructors. Follow-up data will be collected at 3 and 6 months.

At the end of the study, the program instructors, and select clinic personnel will be interviewed to identify successful and unsuccessful elements of implementing the protocol. Strategies for scale up will be identified. In addition, all participants will be interviewed upon completion of their 6 month data collection about their experience and satisfaction with the program. These interviews will be conducted by trained RA's who have not participated in any of the intervention protocol. We will carefully record any implementation issues.

Efficacy data will be collected at the clinic by a trained RA, blinded to participant group assignment and includes clinical (A1C, BMI, WC, BP), T2D self-management, dietary intake, physical activity, and self-efficacy data. All of this data will be collected three times, at baseline, 2-3 months, and 6 month follow-up. We will also collect data on depressive symptoms and food security at all three data collection time points. *A1C* is our primary outcome and will be measured using standard disposable analysis methods. *BMI* will be calculated according to the formula, BMI = kg/m² using a calibrated electronic scale and a portable stadiometer. WC will also be recorded using standard measurement practices. *Systolic and diastolic BP* will be measured according to practice standards. Two readings separated by 1 minute will be averaged. We will also collect data on change in medical status, medication and dosage via the medical record.

Self-management will be measured by the Summary of Diabetes Self-Care Activities questionnaire, a multi-dimensional 12-item scale with items on general diet, specific diet, monitoring blood glucose, foot care, and smoking. Reliability and validity have been established in Spanish-speaking adults. This self-report questionnaire was used successfully in the initial *Yo Puedo!* study.

Dietary intake will also be evaluated by a one-day diet history. While there is no gold standard for self-report of dietary intake, the validity of Spanish dietary recall has been established. This diet history guide captures time, location, type of food and preparation, and amount consumed in past 24 hours. Calories, %fat intake, and fruit and vegetable intake will be calculated. We will

also assess diet intake with a brief modified version of a food frequency questionnaire which asks about how often a variety of foods was eaten in the past month, including culture specific foods. We will include a question regarding food label usage at the end of this questionnaire as the Yo Puedo curriculum teaches how to read food labels and emphasizes their use.

Physical activity will also be measured by accelerometer, using the Actigraph Actigraphy, a 3-axial accelerometer. The advantages of this accelerometer are wrist placement, continuous wear, water resistance and high data storage capacity. Wearing motion sensors day and night has been shown to increase adherence. Accelerometers estimate PA by measuring body movement and can capture frequency, duration and intensity of PA. Units of acceleration are expressed in meters per second squared and transformed into counts per second/minute/day. Cut-points converting counts into moderate-vigorous physical activity have been established (> 1535 counts = moderate PA; 3960 counts = vigorous PA). Both count data and cut-point data per day/week will be used in the analysis. Non-wear time will be calculated using established procedures and considered missing data. Three-axial accelerometers demonstrate excellent reliability with no evidence to suggest differences in brand or type of sensor. Participants will be asked to wear the accelerometer continuously for 1 week at each wave of data collection (baseline, 2-3 months, and 6 months). We will also assess physical activity with the Global Physical Activity Questionnaire developed by the World Health Organization. It is a 16-item questionnaire that assesses physical activity and sedentary behavior that has established reliability and validity.

Self-efficacy will be measured by the Stanford Diabetes Self-Efficacy Scale, an 8-item scale specific to T2D self-management self-efficacy. Items include confidence in exercise, interpreting blood glucose levels, and following dietary recommendations. Reliability and validity have been established in Spanish-speaking adults. This questionnaire was used successfully in the initial *Yo Puedo!* study.

Food Security will be measured using a version of the Latin American and Caribbean Food Security Scale (ELCSA) modified for use in urban older adults. This validated questionnaire contains 8 items that assess financially based food insecurity in households. It includes items related to the frequency at which a household has not been able to access enough food in the last 3 months. This version specifically modifies the questions for better comprehension in older urban Mexican adults of low socioeconomic status, which matches the target population of this study. An additional question to assess diabetes-related food insecurity will also be included.

Health information will be collected in a form which asks about any clinic visits, emergency room visits, episodes of hypoglycemia, diabetes-related health symptoms, medications, other health diagnoses, and A1C and blood pressure results in the previous 3 months. We will also collect data on participant demographics (age, gender, race/ethnicity, income) and depressive symptoms. We will use the Patient Health Questionnaire-8 (PHQ-8) to evaluate depressive symptoms, a well-established measure, with excellent reliability and validity in English and Spanish-speaking adults.

STATISTICAL ANALYSIS PLAN

To evaluate the preliminary efficacy of the program, initially the sample and variables will be described using frequency distributions and appropriate summary statistics. Additionally, the 2 groups will be compared to make certain that randomization procedures were adequate. If any baseline variables differ by group assignment, they will be included as covariates in subsequent analyses. The hypothesis that adults with T2D who receive the *Yo Puedo!* + mHealth will demonstrate better outcomes than adults with T2D in the control condition will be tested using Generalized Linear Mixed Models (GLMM) with an intent-to-treat analysis. While it is likely that significant main effects may not be found for all variables due to the sample size, identification of trends of significance (e.g., p<.10) and effect sizes will be possible. The results of analyses of the clinical outcomes of A1C and BP will require control for the impact of medication usage and dosage change (e.g., change in medications or dosage or no change, increased levels or not, and decreased levels or not).

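### Covariates enter only on chance baseline differences, and nothing in the plan secures adjustment for each outcome's own baseline value in the GLMM

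*Combined protocol and SAP*

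**What the plan says.** The Statistical Analysis Plan first compares the arms at baseline. The stated purpose is that "the 2 groups will be compared to make certain that randomization procedures were adequate". It then gives the covariate rule: "If any baseline variables differ by group assignment, they will be included as covariates in subsequent analyses". No test, threshold or list of variables accompanies it.

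The efficacy hypothesis is "tested using Generalized Linear Mixed Models (GLMM) with an intent-to-treat analysis". The model's fixed effects, time terms, covariance structure and contrast are not given, and the only kind of effect named is a main effect. One further adjustment is named, for two outcomes: "The results of analyses of the clinical outcomes of A1C and BP will require control for the impact of medication usage and dosage change".

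The Design section describes 1:1 computer-generated block randomization and states that "Sequentially numbered opaque sealed envelopes will be used to conceal the allocation determination". It names A1C as the primary outcome. Of the efficacy measures it says "All of this data will be collected three times, at baseline, 2-3 months, and 6 month follow-up", so each outcome's baseline value will be in hand.

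The stated output of the efficacy analysis is modest: "identification of trends of significance (e.g., p<.10) and effect sizes will be possible".

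**The concern.** If concealed random allocation is carried out as described, any baseline difference between the arms is a chance difference. A rule keyed to such differences selects covariates by accident rather than by how well they predict the outcome. Because a difference is not defined, the model cannot be written down before the data are seen.

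The more important gap is what the rule leaves out. An outcome's own baseline is usually among its strongest predictors, and it is already measured here. Yet the plan makes it a covariate only when the arms happen to differ on it. Baseline might also enter the GLMM as one of three repeated responses, but the plan does not say so.

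The stake is precision. A 60-person pilot that intends to report trends at p<.10 and effect sizes depends on it directly.

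**Working it through.** The plan gives no effect size, SD, alpha, power, dropout or correlation, so it has no figure of its own to reproduce. The calculation below is illustrative.

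**Inputs.** From the documents: 60 participants randomized 1:1, so n = 30 per arm. Assumed: no dropout, independent participants, effect d = 0.5 SD, equal SD at each visit, baseline-follow-up correlation r = .5/.6/.7/.8, and no medication adjustment. Sessions are delivered in groups, so the absolute powers are not this trial's power; the comparison between methods is the point.

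**1. Variance of the effect estimate (units of SD²).**
- Three-wave model with a separate group effect at each visit, contrast at follow-up minus baseline. With complete data and an unstructured covariance this is the difference in mean change: (2/n) × 2(1 − r).
- Baseline always adjusted (ANCOVA): (2/n)(1 − r²) × (1 + 1/56). The last factor, 1.018, is the average cost of estimating the slope, with 2n − 4 = 56.
- Ratio: 2(1 − r)/(1 − r²)/1.018 = [2/(1 + r)]/1.018.

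| r | 2/(1 + r) | ÷ 1.018 | excess variance |
|---|---|---|---|
| .5 | 1.333 | 1.31 | 31% |
| .6 | 1.250 | 1.23 | 23% |
| .7 | 1.176 | 1.16 | 16% |
| .8 | 1.111 | 1.09 | 9% |

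Simulation of 200,000 trials per setting gives the same ratios.

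**2. Power at d = 0.5.** The change contrast uses noncentrality 0.5/√[(2/30) × 2(1 − r)], for example 0.5/0.258 = 1.94 at r = .5, with 58 degrees of freedom. ANCOVA uses its own variance with 57.

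| r | change, .05 | always adjusted, .05 | change, .10 | always adjusted, .10 |
|---|---|---|---|---|
| .5 | 48% | 59% | 61% | 71% |
| .6 | 57% | 66% | 69% | 77% |
| .7 | 69% | 75% | 80% | 84% |
| .8 | 85% | 88% | 92% | 93% |

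**3. What the rule recovers.** This depends on how a flagged baseline is used.
- Added as a main-effect covariate while baseline stays a response: it is constant within a person and cancels from the within-person contrast. Generalized least squares with three visits and compound symmetry confirms this. At r = .5 the contrast variance is 0.0667 with or without the covariate. The rule recovers nothing, and the excess stays at 31%/23%/16%/9%.
- Analyst switches from a change score to ANCOVA when baseline is flagged at p<.05: simulated excess 23%/16%/11%/7%.

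**4. Other readings of the GLMM.**
- All three visits as responses with a common baseline mean: variance 0.0500 at r = .5, and 0.0667/0.0500 = 1.333 = 2/(1 + r). This model has the efficiency of ANCOVA, so the loss is about nil.
- Baseline ignored, follow-up values only: ratio [1/(1 − r²)]/1.018 = 1.31/1.54/1.93/2.73. With the rule at p<.05 the simulated ratio is 1.23/1.39/1.68/2.26.

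**5. Type I error.** Simulated null rejection at nominal .05 is 4.3% to 4.8% for the switching version of the rule, and 4.9% to 5.1% for ANCOVA.

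**6. Stability of the covariate set.** With k independent baseline variables screened at p<.05, P(at least one flagged) = 1 − .95^k. For k = 10 this is 40%; for k = 20 it is 64%. Correlation between variables lowers it. The documents do not say which variables are screened, so k is an assumption.

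**The case against.** The strongest reply is that omission is not shown. Outcomes are collected at baseline and two follow-ups and a mixed model is named, so baseline may already be in the model as a response, and one such model loses almost nothing. That stands as a limit on the size of the loss. It does not close the gap, because the plan does not say which model is meant, and an ordinary three-wave group-by-time contrast still carries the loss in the first table.

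A second reply is that this is a feasibility pilot whose SAP already warns that significance may be missed, and that the gain is small at high correlation: at r = .8 the power difference at .05 is 3 points. That is fair, and it keeps the point well short of a fatal flaw. A third is that the baseline comparison is meant to check the allocation procedure. It may stay as description; the gain does not require removing it.

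Three stronger readings are tempting and are not supported:
- That choosing covariates this way inflates false positives. Simulated rejection under the null is at or slightly below nominal.
- That the rule causes the precision loss. The loss comes from not always adjusting for baseline; the rule leaves it unchanged or recovers a little, so deleting the rule alone gains nothing.
- That baseline A1C is disregarded in 95% of trials. The 5% concerns entry as a covariate only. Likewise, the 40% to 64% flagging rate shows an unstable covariate set, not bias.

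**Conclusion.** The point holds as a gap in specification with a cost in precision. The plan admits covariates only on chance imbalance, leaves that criterion undefined, and does not secure adjustment for any outcome's own baseline. Under the three-wave group-by-time reading the excess variance is about 31% at r = .5, falling to 9% at r = .8, and the loss of power at .05 falls from about 11 points to 3. The size could be larger if baseline is ignored altogether, or about nil with a common baseline mean; the documents do not settle which applies.

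All magnitudes rest on the assumed effect, correlations, independence and complete follow-up. For A1C and blood pressure they also leave out the planned medication adjustment, which is not assessed here. The change is worth making because it uses data already collected, and because trends and effect sizes are what the efficacy analysis sets out to deliver.

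**What to change.** Replace the covariate-selection sentence in the Statistical Analysis Plan with wording such as:

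> Every efficacy model adjusts for the baseline value of that outcome, whatever the observed balance, either (a) with only the 3- and 6-month visits as responses and the baseline value as a covariate, or (b) with all three visits as responses and a common baseline mean for both arms. The treatment effect is the between-arm difference at each follow-up. Baseline characteristics are tabulated by arm and are not used to select covariates. Any further covariate, beyond the medication adjustment this plan already names, is fixed before outcome data are analysed by arm.

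The sponsor should choose (a) or (b) and name it. In (a), restricting the responses to follow-up visits is essential: a baseline covariate added while baseline remains a response leaves the whole loss in place.

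The cost is SAP wording only. No new data, participants or procedures are needed.

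### Only the intervention arm is taught in classes and the GLMM's random effects are unstated; a participant-only fit would understate the standard error if classmates' outcomes correlate

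*Combined protocol and SAP*

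**What the plan says.** Sixty adults are individually randomized 1:1 (DESIGN). The program consists of six "interactive group-based sessions (plus an initial orientation session) led by the program instructors" (DESIGN, Interventions). On timing, the randomization paragraph states: "After a group of 5 participants have been randomized to the" intervention condition, the program begins. Five is a trigger for starting; no maximum class size is given.

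Controls are not taught in groups during the comparison: "The wait-list control condition group will receive a handout on T2D self-management" (DESIGN, Interventions), and "Those in the control group will be invited to participate in the program after completion of the 6-month data collection" (DESIGN).

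On measurement: "All of this data will be collected three times, at baseline, 2-3 months, and 6 month follow-up" (DESIGN, efficacy data). The hypothesis concerns the arm difference at 3 and 6 months.

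The Statistical Analysis Plan says that this hypothesis "will be tested using Generalized Linear Mixed Models (GLMM) with an intent-to-treat analysis". It adds covariates for baseline imbalance and, for A1C and blood pressure, for medication change. It states no random effects, no class or clinic term and no covariance structure. On how results will be read: "While it is likely that significant main effects may not be found for all variables due to the sample size", yet "identification of trends of significance (e.g., p<.10) and effect sizes will be possible".

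**The concern.** People taught together share an instructor, a schedule and each other, so their outcomes may be more alike than those of people in different classes. Here that can happen in one arm only. The mean of 30 intervention participants then carries less information than the mean of 30 independent people, while the control mean does not lose any.

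A mixed model can account for this, but only if it has a class term. With three visits per person, the obvious way to fit the GLMM as described is with a participant random effect and nothing else. That handles correlation between one person's visits and ignores correlation between classmates. An analyst could follow the plan to the letter and obtain p-values that are too small.

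The plan intends to pick out trends at p<.10 over many outcomes. That reading, and any interval put around an effect size, is what a later trial would build on.

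The plan also refers to main effects while the hypothesis is about two follow-up times. This matters here because the size of the error depends on which contrast is tested.

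**Working it through.** The plan gives no power calculation, ICC or standard error, so there is no figure of its own to reproduce.

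**Inputs from the documents.** 60 randomized 1:1, so 30 per arm. Classes start at 5, so 30/5 = 6 classes if they stay at that size. Three visits. Classes in the intervention arm only. Trend threshold .10.

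**Assumptions, since the documents give none.** Class ICC 0.02 to 0.20, defined on the variance at one follow-up visit. Correlation between a person's visits r = 0.6. Total variance 1 at each visit in both arms. The class effect is absent at baseline and the same at both follow-ups. Two-sided tests, no dropout.

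**Formulas.** Let m be the class size and s = √(1−ICC). VR is the true variance of the arm difference divided by the variance that a class-ignoring analysis assumes.

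- Single visit: VR = [2 + (m−1)·ICC]/2.
- Change to 6 months, using its own variance: V_I = 2 − 2rs in the intervention arm and V_C = 2 − 2r = 0.8 in controls. VR = [V_I + V_C + (m−1)·ICC]/[V_I + V_C].
- Arm main effect over three visits: the class effect touches two of three visits, so its variance in a person's mean is (4/9)·ICC. M_I = [1 + 2s² + 2r(2s + s²)]/9 + (4/9)·ICC and M_C = (3 + 6r)/9 = 0.7333. VR = [M_I + M_C + (m−1)(4/9)·ICC]/[M_I + M_C].
- Actual type I error = 2·[1 − Φ(z/√VR)], with z = 1.960 (nominal 5%) or 1.645 (nominal 10%).

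**Worked example: 6-month change, ICC 0.10, m = 5.** s = √0.90 = 0.9487. V_I = 2 − 1.2 × 0.9487 = 0.8616. VR = (0.8616 + 0.8 + 4 × 0.10)/(0.8616 + 0.8) = 2.0616/1.6616 = 1.241. √VR = 1.114 and 1.960/1.114 = 1.760, which gives 7.9%.

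**Results, 6 classes of 5** (VR; error at nominal 5% / nominal 10%):

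| ICC | Main effect | Single visit | 6-month change |
|---|---|---|---|
| 0.02 | 1.024; 5.3 / 10.4% | 1.040; 5.5 / 10.7% | 1.050; 5.6 / 10.8% |
| 0.05 | 1.061; 5.7 / 11.0% | 1.100; 6.2 / 11.7% | 1.123; 6.4 / 12.1% |
| 0.10 | 1.122; 6.4 / 12.0% | 1.200; 7.4 / 13.3% | 1.241; 7.9 / 14.0% |
| 0.20 | 1.244; 7.9 / 14.0% | 1.400; 9.8 / 16.4% | 1.463; 10.5 / 17.4% |

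**Simulation check** (100,000 to 200,000 trials per setting, no true average effect). At ICC 0.05 / 0.10 / 0.20 and nominal 5%:

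- Main effect: 5.6–5.8 / 6.4–6.5 / 7.7–8.0%.
- 6-month change with its own variance: about 6.4 / 8.0 / 10.6%.
- 6-month contrast with one residual variance pooled over visits: up to about 6.6 / 8.4 / 11.7%.
- ICC 0: 5.0%, so the excess comes from class.

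**Larger classes.** With 3 classes of 10, the simulated main-effect error is about 6.7 / 8.5 / 11.8%.

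**Does a class-aware test hold its level?** Comparing class-mean changes with individual control changes, with Satterthwaite degrees of freedom, gives 5.1–5.4% with 6 classes. With 3 classes it still runs at about 6–7%.

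**The case against.** The strongest reply is that the faulted model is assumed, not planned. The plan says only GLMM, and a GLMM can hold a class term. That stands. A reader might infer that the sponsor has decided to ignore class; the documents do not show this. They leave the choice open, and every inflation figure above applies only if participant effects are fitted alone. Leaving it open is still a gap, because nothing in the plan steers the analyst to the class term or secures the class identifier that it needs.

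A second reply concerns size. A reader might take the highest figures as the expected error, and the documents do not support that. Part of the 6-month excess with a pooled residual (11.7% against 10.6% at ICC 0.20) comes from that covariance choice and not from class. The ICC is also defined at one visit: on the scale of change, 0.20 becomes 0.20/0.927 = 0.22 at r = 0.6. At r = 0.8 it becomes 0.35, because 2 − 1.6 × 0.8944 = 0.569 and 0.20/0.569 = 0.35. Errors at high visit correlation therefore presuppose heavy clustering. Classes last six weeks, while texts and glucose monitors go to individuals, so the ICC at 6 months may be low.

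Third, this is a pilot with preliminary efficacy aims, and the plan itself expects that not every main effect will reach significance. That limits the weight of the point. A reader might also infer that the effect estimates are biased or that 60 is too few. Neither follows: clustering leaves the point estimates essentially unchanged, and no sample-size calculation is given that could be called wrong.

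Fourth, a model with participant, class and clinic terms at follow-up is heavy for 60 people in up to 10 clinics. This is fair, and a clinic term should be conditional.

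**Conclusion.** The point holds as a specification gap with a known direction. Classes exist in one arm only before month 6, no random effects are named, and a participant-only fit understates the standard error of the arm difference for any positive class ICC.

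The size rests on an ICC, class size and visit correlation that the documents do not give. With 6 classes of 5 and r = 0.6, it is negligible at ICC 0.02 or below and modest at 0.05. At 0.10 to 0.20 it is material for a 6-month contrast. It is smaller for an arm main effect throughout, and larger if classes grow beyond 5.

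What is affected is the p-values, the p<.10 trend reading and any interval reported with the effect sizes. The point should be addressed before analysis. Confidence in the size is medium: the omission is plain, but its consequence depends on the assumptions above.

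**What to change.** 1. Record the assigned class for every intervention participant, including those who never attend, and the clinic for everyone. Attendance is already to be recorded, so this adds little work.
2. In the Statistical Analysis Plan, name the contrast: the arm difference at 3 months and at 6 months.
3. Specify a participant random effect, plus a class random effect in the intervention arm only that acts on the follow-up visits, with Satterthwaite or Kenward-Roger degrees of freedom. A simpler alternative is to compare class-mean changes with individual control changes.
4. Add a clinic term if classes coincide with clinics and the number of clinics permits. The documents do not say how classes map to clinics.
5. If a class ICC is reported, give its interval and say that it is imprecise.

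**Cost.** For the class-mean test with 6 classes of 5 and ICC 0 / 0.05 / 0.10 / 0.20, the 95% interval for 6-month change is wider than one that ignores class by a median of about 2–3 / 10–11 / 17–19 / 30–34%. The range reflects whether the class-ignoring interval uses the change's own variance or a pooled residual. Median degrees of freedom fall from 58 (own-variance analysis) to between 11 and 18. Most of the extra width at higher ICC is uncertainty that the participant-only interval hides.

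In the mixed model, the class variance will be poorly estimated with about 6 classes and often comes out as zero, and the test may be slightly conservative at low ICC. With only 3 classes, a class-level test remains mildly anti-conservative.
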